4. STUDY POPULATION

4.1. Number of Patients

It is anticipated that approximately 30 patients (at least 20 with BBS and at least 6 with AS) will be enrolled and randomized across approximately 10 centers worldwide. Given the rare incidence of these diseases, if additional patients are identified, they may be enrolled as available to gain additional experience.

The specific inclusion and exclusion criteria for enrolling patients in this study are presented in the sections below. As these diseases are ultra-rare, identification of patients is extremely difficult. Therefore, any criteria not fulfilled by a patient with a confirmed BBS or AS diagnosis will be reviewed with the Sponsor. Assuming no severe health concerns, a joint determination will be made regarding the acceptability of enrolling patients not fulfilling all criteria on a case by case basis. Any exceptions to the inclusion and exclusion criteria will be documented in writing and approved by the Sponsor prior to dosing the patient.

4.2. Inclusion Criteria

1. BBS clinical diagnosis as per Beales, 1999 (with either 4 primary features or 3 primary and 2 secondary features from table below)

Bardet-Biedl Syndrome			
Primary Diagnostic Criteria			
Rod cone dystrophy	Learning disabilities		
Polydactyly	Hypogonadism in males		
Obesity	Renal anomalies		
Secondary Diagnostic Criteria			
Speech disorder/delay	Mild spasticity (especially lower limbs)		
Strabismus/cataracts/astigmatism	Diabetes mellitus		
Brachydactyly/syndactyly	Dental crowding/hypodontia/small roots/high arched palate		
Developmental delay	Left ventricular hypertrophy/congenital heart disease		
Polyuria/polydipsia (nephrogenic diabetes insipidus)	Hepatic fibrosis		
Ataxia/poor coordination			
Source: Beales 1999			

Or AS diagnosis as per Marshall, 2007 (using major and minor age adjusted criteria in the table below).

Alström Syndrome				
Diagnostic Criteria				
Major	Minor	Minimum Required		
For patients 6 to ≤14 years of age				
Mutation of ALMS1 and/or family history of AS	Obesity and/or insulin resistance and/or T2DM	2 major criteria or		
 Vision (nystagmus, photophobia, diminished acuity, if old enough for testing: cone dystrophy by ERG) 	 History of DCM/CHF Hearing loss Hepatic dysfunction Renal failure Advanced bone age 	1 major and 3 minor criteria		
For	patients ≥15 years of age	•		
 Mutation of ALMS1 and/or family history of AS Vision (history of nystagmus in infancy/childhood, legal blindness, cone and rod dystrophy by ERG) 	Obesity and/or insulin resistance and/or T2DM History of DCM/CHF Hearing loss Hepatic dysfunction Renal failure Short stature Males: hypogonadism Females: irregular menses and/or hyperandrogenism	2 major and 2 minor criteria or 1 major and 4 minor criteria		

Abbreviations: CHF = congestive heart failure; DCM = dilated cardiomyopathy; ERG = electroretinography; T2DM = Type 2 diabetes mellitus

- Note: at least 90% of patients with BBS and 100% of patients with AS must have genetically confirmed diagnosis at the time of enrollment
 - A genetically confirmed diagnosis of BBS is defined as a homozygous or compound heterozygous loss-of-function mutation in BBS genes; patients without a genetically confirmed BBS diagnosis must be reviewed with the Sponsor's medical monitor prior to enrollment.
 - A genetically confirmed diagnosis of AS is defined as a homozygous or compound heterozygous loss-of-function mutation in the ALMS1 gene.

Once 10% of patients without a confirmed BBS diagnosis have been enrolled in the study, sites will be notified that only genetically confirmed BBS patients may be enrolled.

- 2. ≥ 6 years of age.
- 3. Obese, defined as BMI \geq 30 kg/m² for patients \geq 16 years of age or weight >97th percentile for age and sex on growth chart assessment for patients 6 to 15 years of age.
- 4. Study participant and/or parent or guardian is able to communicate well with the Investigator, to understand and comply with the requirements of the study, and is able to understand and sign the written informed consent/assent.
- 5. Female participants of child-bearing potential must be confirmed non-pregnant and agree to use contraception as outlined in the protocol. Female participants of non-childbearing potential, defined as: surgically sterile (status post hysterectomy, bilateral oophorectomy, or bilateral tubal ligation), post-menopausal for at least 12 months (and confirmed with a screening follicle stimulating hormone (FSH) level in the post-menopausal lab range), or

- failure to have progressed to Tanner Stage V and/or failure to have achieved menarche, do not require contraception during the study.
- 6. Male participants with female partners of childbearing potential must agree to use a double barrier method contraception if they become sexually active during the study or within 90 days following their participation in the study. Male patients must also not donate sperm during and for 90 days following their participation in the study.

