 Obesity and/or insulin resistance and/or T2DM History of DCM/CHF Hearing loss Hepatic dysfunction Renal failure Short stature Males: hypogonadism Females: irregular menses and/or hyperandrogenism 	2 major and 2 minor criter or 1 major and 4 minor criter
	•
	ents ≥15 years of age Obesity and/or insulin resistance and/or T2DM History of DCM/CHF Hearing loss Hepatic dysfunction Renal failure Short stature Males: hypogonadism

or AS diagnosis as per Marshall, 2007 (using major and minor age adjusted criteria in the table below).

- Note: at least 90% of patients with BBS and 100% of patients with AS must have genetically confirmed diagnosis at the time of enrollment
 - A genetically confirmed diagnosis of BBS is defined as a homozygous or compound heterozygous loss-of-function mutation in BBS genes; patients without a genetically confirmed BBS diagnosis must be reviewed with the Sponsor's medical monitor prior to enrollment.
 - A genetically confirmed diagnosis of AS is defined as a homozygous or compound heterozygous loss-of-function mutation in the ALMSI gene

Once 10% of patients without a genetically confirmed BBS diagnosis have been enrolled in the study, sites will be notified that only genetically confirmed BBS patients may be enrolled.

- 2. ≥ 6 years of age.
- 3. Obese, defined as BMI ≥30 kg/m² for patients ≥16 years of age or weight >97th percentile for age and sex on growth chart assessment for patients 6 to 15 years of age.
- Study participant and/or parent or guardian is able to communicate well with the Investigator, to understand
 and comply with the requirements of the study, and is able to understand and sign the written informed
 consent/assent.
- 5. Female participants of child-bearing potential must be confirmed non-pregnant and agree to use contraception as outlined in the protocol. Female participants of non-childbearing potential, defined as: surgically sterile (status post hysterectomy, bilateral oophorectomy, or bilateral tubal ligation), post-menopausal for at least 12 months (and confirmed with a screening follicle stimulating hormone (FSH) level in the post-menopausal lab range), or failure to have progressed to Tanner Stage V and/or failure to have achieved menarche, do not require contraception during the study.

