Study Week	-3	1	2	3	7	11	15	15	17	23	29	35	41	47	53
Study Day	(n/a)	1	8	15	43	71	99	106	113	155	197	239	281	323	365
Injection site inspection ²¹		Χ		X	X	X	X		X	X	X	X	X	X	X
Concomitant medications review	Х	Χ	X	X	X	X	X	X	X	Χ	Χ	X	X	Χ	X
Nutritional counselling and monitoring	Х	Х		Х	Х	Х	Х		Χ	Χ	Х	Х	Х	Х	Х

- † Assessment/sample should be performed/obtained prior to administration of study drug.
- 1 A blood sample will be obtained at Screening to confirm a genetic diagnosis of AS or BBS. However, patients may be entered into the study based on clinical diagnosis of BBS (≤10% of BBS patients) or prior genetic diagnosis of BBS (≥90% of BBS patients) or AS (100% of AS patients) (refer to Section 4.2). This sample may also be used for genotyping other obesity-related genes. The DNA will not be studied or "typed" for any other purpose, unless patients are re-consented.
- 2 Extra retain samples will consist of 2 serum and 2 plasma (K2EDTA) vacutainer tubes and two 5ml urine tubes.
- 3 A comprehensive skin evaluation will be performed by a dermatologist. Any concerning lesions identified during the screening period will be biopsied and results known to be benign prior to first dose of setmelanotide. If the pre-treatment biopsy results are of concern, the patient will be excluded from the study.
- 4 A urine pregnancy test may be performed in order to expedite availability of results prior to dosing on Day 1. All other pregnancy tests will be serum; dosing may continue with results pending.
- 5 Patients/caretakers will draw up and self-administer/administer the drug once daily in the morning beginning the morning of Day 1 and for the duration of dosing. On days with clinic visits, the patients/caretakers will administer the drug in the clinic in the presence of the clinical staff to assure proper technique. Patients/caretakers will return all used vials to the clinic when they visit (the number recorded) and both clinic administered study drug, as well as outpatient study drug administration will be recorded in a study diary.

⁸ Daily hunger questionnaire scores will be recorded on a daily basis, prior to the patient's morning meal. If the patient is unable to assess their own hunger due to impaired cognitive function, a parent/caregiver assessment of hyperphagia will be completed instead (see Appendix 11.5.2).

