6.2. Patient Requirements

6.2.1. Contraception

Setmelanotide has not been completely evaluated in nonclinical Developmental and Reproductive Toxicology Studies to date; therefore, the effects of setmelanotide on embryo-fetal development are unknown at this time. It is imperative all study patients adhere to the contraception requirements as outlined below.

Females must not be pregnant and must have a negative serum pregnancy test result at the Screening Visit and negative urine pregnancy test on Day 1, with results known prior to initiating dosing; pregnancy testing will be monitored during the study.

For female patients who are able to bear children, a highly reliable form of contraception must be used/practiced throughout the study and for 90 following the study. Highly reliable acceptable for of contraception include: hormonal (ie, oral, implantable, or injectable) and single-barrier method (ie, condom), or an Intrauterine Device (IUD) and single-barrier method (ie, condom) or vasectomized partner. True abstinence is acceptable only if it is the preferred and usual lifestyle of the patient.

Females of non-childbearing potential, defined as surgically sterile (status post hysterectomy, bilateral oophorectomy, or bilateral tubal ligation) post-menopausal for at least 12 months (and confirmed with a screening FSH level in the post-menopausal range), or failure to have progressed to Tanner Stage V and/or failure to have achieved menarche, do not require contraception during the study. Younger female patients who are not sexually mature will be assessed for Tanner staging and advised accordingly.

It is not known if this treatment will affect spermatogenesis. Therefore, males with female partners of childbearing potential must agree to use contraception (eg, if they have not had a vasectomy then should either (a) abstain from reproductive sexual intercourse or (b) use a double barrier method (ie, condom and diaphragm and spermicide) if they become sexually active during the study and for 90 days following the study. Male patients must not donate sperm for 90 days following their participation in the study.

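### The puberty clause exempts any female below Tanner V, so read literally a menstruating Tanner III–IV adolescent needs no contraception

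*Protocol*

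**What the plan says.** Three places in the protocol define females of non-childbearing potential: synopsis inclusion criterion 5, Section 4.2 criterion 5, and Section 6.2.1. Each lists surgical sterility, then post-menopausal status confirmed by FSH, then a puberty clause. In Section 4.2 that clause and its consequence read "failure to have progressed to Tanner Stage V and/or failure to have achieved menarche, do not require contraception during the study". The synopsis has the same words, and Section 6.2.1 repeats the definition: "post-menopausal range), or failure to have progressed to Tanner Stage V and/or failure to have achieved menarche". The three copies agree.

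Section 6.2.1 also states a general rule: "For female patients who are able to bear children, a highly reliable form of contraception must be used/practiced throughout the study". It gives the reason, namely that "the effects of setmelanotide on embryo-fetal development are unknown at this time", and treats adherence to the contraception requirements as imperative.

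Other relevant provisions:

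- Section 6.2.1 requires a negative serum pregnancy test at screening and a "negative urine pregnancy test on Day 1, with results known prior to initiating dosing", with further testing during the study.
- Footnote 4 to Protocol Table 2 adds: "All other pregnancy tests will be serum; dosing may continue with results pending".
- Section 6.2.1 says younger females who are not sexually mature will be Tanner-staged and given advice on that basis.
- On abstinence, Section 6.2.1 says: "True abstinence is acceptable only if it is the preferred and usual lifestyle of the patient".

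**The concern.** Menarche and Tanner V are different milestones, and the clause treats falling short of either one as proof that a female cannot conceive. A girl who has reached menarche but is still at Tanner III or IV falls short of the second milestone only. On the wording she is nonetheless classed as of non-childbearing potential and released from contraception.

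The trial can enrol such patients: entry is from age 6, and treatment runs to 66 weeks. What is at stake is patient safety. The protocol says it does not know the drug's effect on a fetus, yet its wording allows a potentially fertile adolescent to be dosed without contraception. No efficacy estimate or error rate is involved.

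**Working it through.** The main check is one of logic. The only arithmetic is on visit spacing.

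**Step 1: the clause.** Let A be *not yet at Tanner V* and B be *no menarche*. The text exempts a female if A and/or B holds.

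| Patient | A | B | Result under the clause |
|---|---|---|---|
| Tanner III–IV, menstruating | true | false | exempt |
| Tanner III–IV, pre-menarche | true | true | exempt |
| Tanner V, no menarche | false | true | exempt |
| Tanner V, menstruating | false | false | contraception required |

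Only the last group must use contraception. With *and* in place of *and/or*, or with menarche as the sole test, the first row would change to contraception required.

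**Step 2: does other text override the clause?**

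- *The general rule in Section 6.2.1.* If ability to bear children means physiological ability, the first-row patient falls under both the rule and the exemption. If it means everyone outside the defined non-childbearing group, the exemption covers her outright. Neither reading clearly requires contraception for her.
- *Tanner staging with advice.* This rests on Tanner stage, the limb that causes the problem. It does not say that menarche ends the exemption, and advice is not a requirement. Section 11.7 also suggests that the child could point to a diagram in place of an examination.
- *Sponsor review of exceptions (Section 4.1).* This applies to criteria a patient does not fulfil. She fulfils criterion 5 as written, so nothing sends her for review.
- *Pregnancy tests.* The entry tests are a real safeguard, because the results must be known before the first dose. Later tests find a pregnancy after exposure has begun.

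**Step 3: how long exposure could last before the next scheduled test.** The study days come from Protocol Tables 2 and 3 and SAP Tables 1 and 2. Telephone contacts (Days 8 and 106) are left out.

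- Period 1: Days 1, 15, 43, 71, 99. Gaps: 14, 28, 28, 28. Longest: 28 days.
- Period 2: Days 99, 113, 155, 197, 239, 281, 323, 365. Gaps: 14, then 42 six times. Longest: 42 days.
- Period 3: Days 365, 414, 462. Gaps: 414 − 365 = 49 and 462 − 414 = 48. Longest: 49 days.

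These figures assume a pregnancy test at every clinic visit, as the SAP schedule shows. They are visit spacing, not an estimate of fetal exposure, and dosing may continue while a result is awaited.

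**The case against.** The strongest reply is that this takes the worst reading of an ambiguous connective. The clause sits under the heading of non-childbearing potential, which a menstruating adolescent does not naturally fit. Section 6.2.1 opens with a mandatory rule that, in ordinary language, would cover her. Sites would stage and advise her individually, and the investigator may refuse anyone judged unsuitable under exclusion 11. A sensible investigator would probably reach the right answer.

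That lowers the practical risk. It does not change what the clause says, and a site that followed the definition literally would be complying with the protocol.

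Three further points stand as limits:

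- Parts of the protocol are not visible, including Section 7 and several assessment sections. Rules on pubertal change during the study or on handling a pregnancy may be there, so nothing is claimed about whether status is reassessed after entry. Repeat Tanner staging would not cure the problem, since the exemption lasts until Tanner V.
- The SAP is based on a protocol dated 26 August 2020 and differs from the supplied protocol, for example in the one-sided alpha (0.025 against 0.05) and the number of key secondary endpoints (three against four). The clause may read differently in another version.
- The number of patients exposed to the gap is unknown and could be zero.

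**Conclusion.** The concern holds as a reading of the supplied protocol. All three copies of the clause exempt a post-menarchal female below Tanner V, and no visible text clearly restores the requirement.

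The size is modest. The documents do not say how many patients are affected. The protocol plans about 30 patients and the SAP's pivotal cohort has 38, of both sexes and from age 6, so the group is probably small. For a patient who is not sexually active the difference is slight, because true abstinence already satisfies the rule where it is her preferred and usual lifestyle. The gap matters for a sexually active, post-menarchal adolescent below Tanner V. For her, exposure could run up to 28, 42 or 49 days, depending on the period, before the next scheduled test.

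This should be corrected on safety grounds. It has no bearing on any statistical result.

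**What to change.** In the synopsis, Section 4.2 and Section 6.2.1, delete the Tanner V limb so that the puberty-based exemption reads: *or who have not achieved menarche, do not require contraception*.

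Then add: *A female who achieves menarche during the study must follow the contraception requirements of Section 6.2.1 from that time; menarche status will be asked at scheduled clinic visits.*

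Tanner staging can stay for growth assessment and advice, but should no longer grant the exemption.

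The cost is one clause in three places and one question at existing visits. The downside is that a few more adolescents come under the requirement, which abstinence can meet on the terms already in Section 6.2.1.

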4.3. Exclusion Criteria

- 1. Recent intensive (within 2 months) diet and/or exercise regimen with or without the use of weight loss agents (including herbal medications) that has resulted in >2% weight loss. These patients may be reconsidered approximately 1 month after cessation of such intensive regimens.
- 2. Current or prior (within prior 2 months) use of any medication, including those approved to treat obesity, that could impact the efficacy results of this study (eg, orlistat, lorcaserin, phentermine-topiramate, naltrexone-bupropion, liraglutide). Patients on a stable dose and regimen (for at least 2 months) of medication to treat attention deficit hyperactivity disorder (ADHD) may be enrolled in the study as long as they agree to remain on the same dose and regimen during the study.
- 3. Prior gastric bypass surgery resulting in >10% weight loss durably maintained from the baseline pre-operative weight with no evidence of weight regain. Specifically, patients may be considered if surgery was not successful, resulted in <10% weight loss compared to pre-operative baseline weight, or there is clear evidence of weight regain after an initial response to bariatric surgery. All patients with a history of bariatric surgery must be discussed with, and receive approval from, the Sponsor prior to enrollment.
- 4. Diagnosis of schizophrenia, bipolar disorder, personality disorder or other Diagnostic and Statistical Manual of Mental Disorders fifth edition (DSM-V) disorders that the Investigator believes will interfere significantly with study compliance. Neurocognitive disorders affecting ability to consent will not be disqualifying as long as an appropriate guardian able to give consent has been appointed.
- 5. In patients with no significant neurocognitive deficits:
 - A PHQ-9 score of ≥15 and/or
 - Any suicidal ideation of type 4 or 5 on the C-SSRS, any lifetime history of a suicide attempt, or any suicidal behavior in the last month.
- Current, clinically significant pulmonary, cardiac, or oncologic disease considered severe
 enough to interfere with the study and/or confound the results. Any patient with a
 potentially clinically significant disease should be reviewed with the Sponsor to
 determine eligibility.
- 7. History of significant liver disease or liver injury, or a current liver assessment due to abnormal liver tests (as indicated by abnormal liver function tests, alanine transaminase [ALT], aspartate transaminase [AST], alkaline phosphatase, or serum bilirubin >1.5× the upper limit of normal [ULN] for any of these tests) for an etiology other than non-alcoholic fatty liver disease (NAFLD). Thus, any underlying etiology besides NAFLD,

including diagnosed non-alcoholic steatohepatitis (NASH), other causes of hepatitis, or history of hepatic cirrhosis is exclusionary, but the presence of NAFLD is not be exclusionary.

- 8. Moderate to severe renal dysfunction defined as <30 mL/min (Appendix 11.6).
- History or close family history (parents or siblings) of skin cancer or melanoma (excluding non-invasive basal or squamous cell lesion), or patient history of ocularcutaneous albinism.
- 10. Significant dermatologic findings relating to melanoma or pre-melanoma skin lesions (excluding non-invasive basal or squamous cell lesion), determined as part of comprehensive skin evaluation performed by a qualified dermatologist during screening. Any concerning lesions identified during the screening period will be biopsied and results must be known to be benign prior to enrollment. If the pre-treatment biopsy results are of concern, the patient should be excluded from the study.
- 11. Patient is, in the opinion of the Study Investigator, not suitable to participate in the study.
- 12. Participation in any clinical study with an investigational drug/device within 3 months prior to the first day of dosing.
- 13. Significant hypersensitivity to study drug.
- 14. Inability to comply with QD injection regimen.

4.4. Patient Identification and Registration

The Investigator and the Investigator's study staff will identify potential patients for the study. Patients who are candidates for enrollment into the study will be evaluated for eligibility by the Investigator to ensure that the inclusion and exclusion criteria have been satisfied and that the patient is eligible for participation in this clinical study.

All patients screened for the study will be assigned a unique screening number representing a combination of the site number and a sequential 3-digit number. Screening numbers will be assigned sequentially starting at 001 (ie, the first patient screened at site 10 would be assigned screening number 10001).

